1.2 Hypothesis

Treatment of critically ill patients with ARF with carbocisteine, hypertonic saline, or both, will lead to increased mucus hydration and changes in sputum viscosity and elasticity.

1.3 **Aim**

To determine if critically ill patients with ARF treated with carbocisteine, hypertonic saline, or both, experience increased hydration of airway mucus (reflected as a reduced percentage mucus solid content¹).

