7. ANALYSIS PRINCIPLES

The primary analysis will be conducted on outcome data from the per-protocol population. Analyses will be two-sided and tested at an *a priori* significance level of p=0.05.

We will describe baseline characteristics and follow-up measurements using suitable measures of central tendencies; means and medians with the associated standard deviations/95% confidence intervals (CI) and interquartile ranges for continuous data; and frequencies and proportions for categorical data (including binary data).

Primary outcome

To measure percentage mucus solid content (dry-to-wet weight ratio) of sputum at Day 0 and Day 3 following commencement of treatment with carbocisteine and/or hypertonic saline.

Analysis

Percent solids (wt%) of sputum will be assessed by measurement of pre- and post-desiccation weights of sputum aliquots. Higher percentage weight indicates greater mucus solid content and is associated with disease² and lower percentage mucus solid content i.e. more hydrated indicates lower solid content which is associated with a more normal phenotype.

We will assess the sputum percent solids in all 4 patient cohorts on the MARCH trial at day 3 and compare to sample measurements at baseline (before commencement of treatment).

Comparisons will be made between the groups. Analysis of Covariance (ANCOVA) (and post-hoc tests if significant differences are identified), or non-parametric equivalents, will be used to detect difference in means adjusting for baseline values.

Secondary outcomes

The secondary outcome measure post commencement of treatment will be to measure:

- 1. Percentage mucus solid content (dry-to-wet weight ratio) of sputum at Day 7 following commencement of treatment with hypertonic saline and/or carbocisteine
- 2. Sputum elasticity (G') and viscosity (G") (and yield stress, T_c) at Day 3
- 3. Sputum IL-6, IL-8 and 8-isoprostane levels at Day 3
- 4. Sputum elasticity (G') and viscosity (G") (and yield stress, T_c) at Day 7
- 5. Sputum IL-6, IL-8 and 8-isoprostane levels at Day 7

Analysis

Percent solids (wt%) of sputum will be assessed at day 7, as for the primary objective analysis, and compared to sample measurements at baseline (before commencement of treatment).

Comparisons will be made between the groups using ANCOVA (and post-hoc tests if significant differences are identified) will be used to detect difference in means adjusting for baseline values.

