Sputum will also be characterized by its elastic (G') and viscous (G'') moduli in order to determine the yield stress value, T_c , a marker of sputum motion. A high T_c , indicates a greater amount of obstruction in the sample and a lower T_c , indicates a decreased amount of obstruction in the sample.

We will assess the sputum elasticity, viscosity and yield stress in sputum samples obtained from all 4 patient cohorts on the MARCH trial at Day 3 and day 7 and compare to sample measurements at baseline (before commencement of treatment).

Doc No: ST06-RD01 Page **11** of **29**

We will also measure sputum levels of IL-6, IL-8 and 8-isoprostane in sputum samples from all 4 patient cohorts on the MARCH trial at Days 3 and 7 and compare to sample measurements at baseline (before commencement of treatment).

Comparisons will be made between the groups using ANCOVA (and post-hoc tests if significant differences are identified) will be used to detect difference in means adjusting for baseline values.

In addition, all analyses will be undertaken by comparison (i.e. Carbocisteine vs No carbocisteine and Hypertonic saline vs No hypertonic saline).

Doc No: ST06-RD01 Page **12** of **29**

[figure not shown]

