8.5 Trial outcomes

Primary Outcome:

Change from day 0 to day 3 in percentage mucus solid content (wt%), mean(SD) by treatment arm, difference in mean with 95% CI.

Comparisons will be made between the groups using ANCOVA (and post-hoc tests if significant differences are identified) will be used to detect difference in means adjusting for baseline values (Day O percentage mucus solid content (wt%)).

Doc No: ST06-RD01 Page 15 of 29

Secondary outcomes:

- Change from day 0 to day 7 in percentage mucus solid content (wt%), mean(SD) by treatment arm, difference in mean with 95% CI.
- Change from day 0 to day 3 in Sputum elasticity (G'), mean(SD) by treatment arm, difference in mean with 95% CI.
- Change from day 0 to day 3 in Sputum viscosity (G"), mean(SD) by treatment arm, difference in mean with 95% CI.
- Change from day 0 to day 3 in yield stress (T_c), mean(SD) by treatment arm, difference in mean with 95% CI.
- Change from day 0 to day 7 in Sputum elasticity (G'), mean(SD) by treatment arm, difference in mean with 95% CI.
- Change from day 0 to day 7 in Sputum viscosity (G"), mean(SD) by treatment arm, difference in mean with 95% CI.
- Change from day 0 to day 7 in yield stress (T_c), mean(SD) by treatment arm, difference in mean with 95% CI.
- Change from day 0 to day 3 in Sputum IL-6, mean(SD) by treatment arm, difference in mean with 95% CI.
- Change from day 0 to day 3 in Sputum IL-8, mean(SD) by treatment arm, difference in mean with 95% CI.
- Change from day 0 to day 3 in Sputum 8-isoprostane, mean(SD) by treatment arm, difference in mean with 95% CI.
- Change from day 0 to day 7 in Sputum IL-6, mean(SD) by treatment arm, difference in mean with 95% CI.
- Change from day 0 to day 7 in Sputum IL-8, mean(SD) by treatment arm, difference in mean with 95% CI.
- Change from day 0 to day 7 in Sputum 8-isoprostane, mean(SD) by treatment arm, difference in mean with 95% CI.

Comparisons will be made between the groups using ANCOVA (and post-hoc tests if significant differences are identified) will be used to detect difference in means adjusting for baseline values.

Will also be presented by comparison

Doc No: ST06-RD01 Page **16** of **29**

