APPENDIX 1: EXAMPLE SUMMARY TABLES

Table x.x.x. Summary statistics for MARCH mucus hydration parameters

	Treatment Group				
	HTS	Carbocisteine	HTS plus Carbocisteine	UACM	
	n= <n></n>	n= <n></n>	n= <n></n>	n= <n></n>	
Sputum day 0					
Dry to wet ratio (wt %)	xx.x (xx.x)	xx.x (xx.x)	xx.x (xx.x)	xx.x (xx.x)	
Sputum elasticity (G') (Pa)	xx.x (xx.x)	xx.x (xx.x)	xx.x (xx.x)	xx.x (xx.x)	
Sputum viscosity (G") (Pa)	xx.x (xx.x)	xx.x (xx.x)	xx.x (xx.x)	xx.x (xx.x)	
Yield stress (Tc) (Pa)	xx.x (xx.x)	xx.x (xx.x)	xx.x (xx.x)	xx.x (xx.x)	
Sputum IL-6 (pg/mL)	xx.x (xx.x)	xx.x (xx.x)	xx.x (xx.x)	xx.x (xx.x)	
Sputum IL-8 (pg/mL)	xx.x (xx.x)	xx.x (xx.x)	xx.x (xx.x)	xx.x (xx.x)	
Sputum 8-isoprostane 9 (pg/mL)	xx.x (xx.x)	xx.x (xx.x)	xx.x (xx.x)	xx.x (xx.x)	
Sputum day 3			·		
Dry to wet ratio (wt %)	xx.x (xx.x)	xx.x (xx.x)	xx.x (xx.x)	xx.x (xx.x)	
Sputum elasticity (G') (Pa)	xx.x (xx.x)	xx.x (xx.x)	xx.x (xx.x)	xx.x (xx.x)	
Sputum viscosity (G") (Pa)	xx.x (xx.x)	xx.x (xx.x)	xx.x (xx.x)	xx.x (xx.x)	
Yield stress (Tc) (Pa)	xx.x (xx.x)	xx.x (xx.x)	xx.x (xx.x)	xx.x (xx.x)	
Sputum IL-6 (pg/mL)	xx.x (xx.x)	xx.x (xx.x)	xx.x (xx.x)	xx.x (xx.x)	
Sputum IL-8 (pg/mL)	xx.x (xx.x)	xx.x (xx.x)	xx.x (xx.x)	xx.x (xx.x)	
Sputum 8-isoprostane 9 (pg/mL)	xx.x (xx.x)	xx.x (xx.x)	xx.x (xx.x)	xx.x (xx.x)	
Sputum day 7	·	·	•		
Dry to wet ratio (wt %)	xx.x (xx.x)	xx.x (xx.x)	xx.x (xx.x)	xx.x (xx.x)	
Sputum elasticity (G') (Pa)	xx.x (xx.x)	xx.x (xx.x)	xx.x (xx.x)	xx.x (xx.x)	
Sputum viscosity (G") (Pa)	xx.x (xx.x)	xx.x (xx.x)	xx.x (xx.x)	xx.x (xx.x)	
Yield stress (Tc) (Pa)	xx.x (xx.x)	xx.x (xx.x)	xx.x (xx.x)	xx.x (xx.x)	
Sputum IL-6 (pg/mL)	xx.x (xx.x)	xx.x (xx.x)	xx.x (xx.x)	xx.x (xx.x)	

Doc No: ST06-RD01 Page **20** of **29**

MARCH EME Statistical Analysis Plan Final 2.0 26/11/2025

Sputum IL-8 (pg/mL)	xx.x (xx.x)	xx.x (xx.x)	xx.x (xx.x)	xx.x (xx.x)
Sputum 8-isoprostane 9 (pg/mL)	xx.x (xx.x)	xx.x (xx.x)	xx.x (xx.x)	xx.x (xx.x)

Doc No: ST06-RD01 Page **21** of **29**

Table x.x.x. Baseline Characteristics at trial entry

	·	HTS	Carbocisteine	HTS plus Carbocisteine	UACM
		n=	n=	n=	n=
Age (years)		xx.x(xx.x)	xx.x(xx.x)	xx.x(xx.x)	xx.x(xx.x)
Sex	Male	n(%)	n(%)	n(%)	n(%)
Sex	Female	n(%)	n(%)	n(%)	n(%)
	White	n(%)	n(%)	n(%)	n(%)
	Black	n(%)	n(%)	n(%)	n(%)
Ethnicity	Asian	n(%)	n(%)	n(%)	n(%)
	Unknown	n(%)	n(%)	n(%)	n(%)
	Other*	n(%)	n(%)	n(%)	n(%)
Temperature(°C)		xx.x(xx.x)	xx.x(xx.x)	xx.x(xx.x)	xx.x(xx.x)
APACHE II Score		xx.x(xx.x)	xx.x(xx.x)	xx.x(xx.x)	xx.x(xx.x)

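### The planned comparison of sputum IL-6, IL-8 and 8-isoprostane cannot separate dilution by the study drugs from a change in inflammation or oxidative stress

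*SAP*

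**What the plan says.** Section 1.2 of the SAP hypothesises that carbocisteine, hypertonic saline or both "will lead to increased mucus hydration and changes in sputum viscosity and elasticity". Section 1.3 aims to find out whether treated patients "experience increased hydration of airway mucus (reflected as a reduced percentage mucus solid content". Section 7 describes the measurement: "Percent solids (wt%) of sputum will be assessed by measurement of pre- and post-desiccation weights of sputum aliquots".

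On the mediators, Section 7 says: "We will also measure sputum levels of IL-6, IL-8 and 8-isoprostane in sputum samples from all 4 patient cohorts", at Days 3 and 7 against baseline. Section 8.5 sets the summary, for example "Change from day 0 to day 3 in Sputum IL-6, mean(SD) by treatment arm, difference in mean with 95% CI", and repeats it for IL-8, 8-isoprostane and Day 7. The model is ANCOVA adjusted for baseline values. Section 7 also asks for each analysis by factor (each drug v no such drug).

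The unit appears only in the first table of Appendix 1, in row labels such as "Sputum IL-6 (pg/mL" and "Sputum IL-8 (pg/mL"; 8-isoprostane has the same unit. Nothing in the SAP relates a mediator to percent solids, total protein or any other dilution marker, and there is no rule for reading a fall in a mediator.

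**The concern.** A value in pg/mL is a mass of mediator divided by a volume of sputum. The treatments are intended to enlarge that volume with water. If they succeed and the mediator mass stays the same, pg/mL falls in the treated arms.

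Adjusting for the Day 0 concentration does not help. It accounts for differences between patients before treatment, whereas this dilution arises after treatment starts and differs by arm precisely when the drug works.

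The mediator results are therefore tied to the primary outcome. When hydration improves, they tend to fall whether or not inflammation or oxidative stress has changed, and a true rise could be hidden in the same way. In a mechanistic study these are the explanations one wants to tell apart. Percent solids is planned at the same three time-points, so the data to do so will exist.

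**Working it through.** **1. The SAP's own sample size (Section 5).** Inputs: difference 1.15 points, SD 2.3, two-sided 0.05, 90% power.

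- n per arm = 2 × (1.960 + 1.282)² × (2.3/1.15)² = 2 × 10.51 × 4 = 84.1, so 85. Power at 85 by the noncentral t is 0.900.
- With 5% dropout, 85/0.95 = 89.5, so 90 per arm and 360 in all.

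The stated figures reproduce. The pooled factor comparisons have 2 × 85 = 170 per side.

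**2. Number of outcomes affected (Section 8.5).** One solids outcome (Day 7), six rheology outcomes and six mediator outcomes (three mediators × two days) make 13. Six of 13 are mediators.

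**3. Size of the dilution.** Let m be mediator mass, s solids mass and W wet mass, with 1 mL taken as 1 g. Concentration is m/W and percent solids is 100 × s/W. Adding water changes only W, so both fall by the same factor. With baseline solids b and a fall of 1.15 points, the factor is (b − 1.15)/b. The SAP gives no mean percent solids, so b is an assumption.

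| Assumed b | Factor | Fall in pg/mL |
|---|---|---|
| 4% | 2.85/4 = 0.713 | 29% |
| 6% | 4.85/6 = 0.808 | 19% |
| 8% | 6.85/8 = 0.856 | 14% |

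**4. Chance of p<0.05 from dilution alone.** The SAP plans differences in means and states no log transformation. The calculation is therefore a simulated ANCOVA on untransformed log-normal values, adjusted for Day 0. The Day 0 correlation (0.4) and the log-scale SD are assumptions, because the SAP gives neither. Ranges cover b from 8% down to 4%.

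| Log SD | 85 v 85 | 170 v 170 |
|---|---|---|
| 1.0 | about 14-45% (22% at b = 6%) | about 22-73% (38% at b = 6%) |
| 1.5 | about 6-14% (8% at b = 6%) | about 9-25% (13% at b = 6%) |

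A repeat run agreed to within about two points. A log-scale t-test would give higher values (28% and 50% at b = 6%, log SD 1.0), but that is not the planned analysis.

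**5. Effect of dividing by solids.** Take 1000 pg/mL at 6% solids: 1000/0.06 = 16,667 pg per gram of solids. After dilution to 4.85% the concentration is 808 pg/mL, and 808.3/0.0485 is again 16,667. Pure dilution cancels.

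**The case against.** A reader might infer that the SAP plans to report an anti-inflammatory or antioxidant effect. It does not. The hypothesis and aim cover hydration and rheology only, the objectives ask for measurement of sputum levels, and Section 7 interprets percent solids and yield stress but not the mediators. What stands against the plan is narrower: the secondary outcome table has a between-arm p-value for each mediator, with nothing to say how it should be read.

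A reader might also infer that pg/mL is fixed as the analysis unit. It appears only in an example descriptive table; Sections 7 and 8.5 and the secondary outcome table give no unit, and Section 3.5 leaves units to the received data tables. The protocol or a laboratory manual, not seen here, could define a correction. Even so, the only unit shown and the only model stated contain none.

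The probabilities should not be read as the trial's false-positive rate. They rest on an assumed mean percent solids, mediator SD and correlation. The pairwise arm tests are post hoc, run only if the overall test is significant. Section 5 expects missing samples at Day 7, so 85 and 170 are too large there. Fewer samples lower the chance of p<0.05 but leave the bias in the estimate.

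The mass balance assumes that all of the fall in solids is added water. If solids fall because less mucin is secreted, pg/mL need not fall.

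Finally, dry weight is not a clean denominator. Salt retained in the two hypertonic saline arms adds to it and lowers the ratio; reduced mucin raises it. This objection stands, and it rules out making the dry-weight scale the sole basis for a conclusion.

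**Conclusion.** The point holds as a limit on interpretation. The SAP intends to add water to the sputum, shows the mediators in pg/mL and adjusts only for Day 0, so six of 13 secondary outcomes can move through dilution alone. At the planning difference this is a fall of about 14-29% for 8% down to 4% solids, if the whole fall in solids is added water. The chance of a nominally significant result from dilution alone then runs from barely above 5% to well above it, depending mainly on mediator variability, which the SAP does not give.

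The documents do not support saying that a false mechanism will be reported, or that the mediator results will be spurious. The primary outcome and its power are not touched. The change is worth making before analysis because it is cheap and the trial is open label.

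**What to change.** In Sections 7 and 8.5 and in the secondary outcome table:

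- Keep the comparison in pg/mL and state the unit.
- Add a prespecified supportive analysis of each mediator per gram of dry weight: the concentration divided by the percent solids of the same patient-day sample, with the same ANCOVA adjusted for the Day 0 value on that scale. This is preferable to adding percent solids as a covariate, because solids after Day 0 is itself an outcome of treatment.
- State that a proportional fall in pg/mL no larger than the fall in percent solids will not be read as reduced inflammation or oxidative stress, and that an effect will be claimed only when both scales agree.
- State the limits. Error in percent solids adds noise, and retained salt or reduced mucin can bias the ratio, so the dry-weight scale is supportive. In the hypertonic saline arms, dilution and retained salt together could lower both scales, so agreement there needs extra caution.

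The cost is SAP wording and one derived variable per mediator. No new samples or assays are needed.

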8. ANALYSIS DETAILS

The results of the analyses will be reported following the principles of the ICH E3 guidelines on the Structure and Content of Clinical Study Reports. Refer to the CONSORT Extensions for various trial designs.

8.1 Recruitment and follow-up patterns

- Recruitment by year, centre.
- Withdrawals by site this should include the timing of withdrawals.

8.2 **CONSORT Flow Diagram**

Doc No: ST06-RD01 Page **13** of **29**

8.3 **Baseline Characteristics**

- Age (years), mean(sd) by treatment arm
- Sex, n(%) by treatment arm
- Ethnicity, n(%) by treatment arm
- Temperature (°C), mean(sd) by treatment arm
- APACHE II Score, mean(sd) by treatment arm
- ABG (Worst)
 - o PaO₂ (kPa), mean(sd) by treatment arm
 - o FiO₂ %, mean(sd) by treatment arm
 - o P/F Ratio (PaO₂/FiO₂), mean(sd) by treatment arm
- ABG (Closest to but prior to randomisation)
 - o PaO₂ (kPa), mean(sd) by treatment arm
 - o FiO₂ %, mean(sd) by treatment arm
 - o P/F Ratio (PaO₂/FiO₂), mean(sd) by treatment arm
 - o PaCO₂ (kPa), mean(sd) by treatment arm
 - Lactate (mmol/L), mean(sd) by treatment arm
 - o pH, mean(sd) by treatment arm
 - o H+ (only record if pH not available), mean(sd) by treatment arm
 - Bicarbonate (mmol/L), mean(sd) by treatment arm

ARF Aetiology

- Main admission diagnosis, n(%) by treatment arm
- Pulmonary/Non Pulmonary Categorisation, n(%) by treatment arm
- o Presence of ARDS, n(%) by treatment arm

Medical History

- Is the patient currently receiving antibiotics to treat a pulmonary infection?, n(%) by treatment arm
- Does the patient have a pre-existing chronic respiratory condition?, n(%) by treatment
- Does the patient have a neurological diagnosis?, n(%) by treatment arm
- Functional Co-morbidity Score, mean(SD) by treatment arm
- Angina, n(%) by treatment arm
- Anxiety or panic disorders, n(%) by treatment arm
- o Arthritis, n(%) by treatment arm
- Asthma, n(%) by treatment arm
- o Chronic Obstructive Pulmonary Disease (COPD); Acquired Respiratory Distress Syndrome (ARDS); or Emphysema, n(%) by treatment arm
- Congestive Heart Failure (or heart disease), n(%) by treatment arm
- Degenerative Disc Disease (Back Disease, Spinal Stenosis or Severe Chronic Back Pain),
 n(%) by treatment arm
- Depression, n(%) by treatment arm
- Diabetes Types I and II, n(%) by treatment arm
- Hearing Impairments (very hard of hearing, even with hearing aids), n(%) by treatment arm
- Heart Attack (Myocardial Infarction), n(%) by treatment arm
- Neurological disease (such as Multiple Sclerosis or Parkinson's Disease), n(%) by treatment arm
- Obesity and/or Body Mass Index > 30 (weight in kg/height in m²), n(%) by treatment arm
- Osteoporosis, n(%) by treatment arm
- o Peripheral Vascular Disease, n(%) by treatment arm

Doc No: ST06-RD01 Page **14** of **29**

- Stroke or Transient Ischaemic Attack, n(%) by treatment arm
- Upper Gastrointestinal Disease (e.g. Ulcer, Hernia, Reflux), n(%) by treatment arm
- o Visual Impairment (e.g. Cataracts, Glaucoma, Macular Degeneration), n(%) by treatment arm
- **Ventilation Parameters**
 - Mode of ventilation, n(%) by treatment arm
 - Minute Volume (ml), mean(sd) by treatment arm
 - Total Respiratory Rate, mean(sd) by treatment arm
 - Plateau Pressure (cmH2O), mean(sd) by treatment arm
 - o PEEP (cmH₂O), mean(sd) by treatment arm
 - Tidal Volume (Minute Volume/Total Respiratory Rate), mean(sd) by treatment arm
 - Respiratory Compliance (ml/cmH2O), mean(sd) by treatment arm
 - Driving Pressure (cmH₂O), mean(sd) by treatment arm
 - Was humidification used?, n(%) by treatment arm
 - Type of humidification, n(%) by treatment arm
- SOFA Score, mean(sd) by treatment arm

Will also be presented by comparison

8.4 Trial treatment

- Number of days on treatment, mean(sd) by treatment arm
- Number of doses, mean(sd) by treatment arm
- Treatment compliance, n(%) by treatment arm
- Reasons for termination of study drug, n(%) by treatment arm
- Did not receive allocated treatment, n(%) by treatment arm
- Received treatment of other group, n(%) by treatment arm
- Antibiotic Usage
 - O Number of patients prescribed antibiotics at least once, n(%) by treatment arm
 - Number of days on antibiotics, mean(sd) by treatment arm
 - o Overall dose (antibiotics), mean (sd) by treatment arm
- **Usual Airway Clearance Management**
 - Number of sessions, mean(sd) by treatment arm
- Non-trial mucoactive administration
 - No. patients with non-trial mucoactive administered, n(%) by treatment arm
 - O Name of mucoactive, n(%) by treatment arm
 - o Total number of days on non-trial mucoactive, mean(sd) by treatment arm
- Consent to Continue/Withdrawal of Consent, n(%) by treatment arm
- Protocol Deviations, no. events (%) by treatment arm, no. patients (%) by treatment arm

Will also be presented by comparison

8.5 Trial outcomes

Primary Outcome:

Change from day 0 to day 3 in percentage mucus solid content (wt%), mean(SD) by treatment arm, difference in mean with 95% CI.

Comparisons will be made between the groups using ANCOVA (and post-hoc tests if significant differences are identified) will be used to detect difference in means adjusting for baseline values (Day O percentage mucus solid content (wt%)).

Doc No: ST06-RD01 Page 15 of 29

Secondary outcomes:

- Change from day 0 to day 7 in percentage mucus solid content (wt%), mean(SD) by treatment arm, difference in mean with 95% CI.
- Change from day 0 to day 3 in Sputum elasticity (G'), mean(SD) by treatment arm, difference in mean with 95% CI.
- Change from day 0 to day 3 in Sputum viscosity (G"), mean(SD) by treatment arm, difference in mean with 95% CI.
- Change from day 0 to day 3 in yield stress (T_c), mean(SD) by treatment arm, difference in mean with 95% CI.
- Change from day 0 to day 7 in Sputum elasticity (G'), mean(SD) by treatment arm, difference in mean with 95% CI.
- Change from day 0 to day 7 in Sputum viscosity (G"), mean(SD) by treatment arm, difference in mean with 95% CI.
- Change from day 0 to day 7 in yield stress (T_c), mean(SD) by treatment arm, difference in mean with 95% CI.
- Change from day 0 to day 3 in Sputum IL-6, mean(SD) by treatment arm, difference in mean with 95% CI.
- Change from day 0 to day 3 in Sputum IL-8, mean(SD) by treatment arm, difference in mean with 95% CI.
- Change from day 0 to day 3 in Sputum 8-isoprostane, mean(SD) by treatment arm, difference in mean with 95% CI.
- Change from day 0 to day 7 in Sputum IL-6, mean(SD) by treatment arm, difference in mean with 95% CI.
- Change from day 0 to day 7 in Sputum IL-8, mean(SD) by treatment arm, difference in mean with 95% CI.
- Change from day 0 to day 7 in Sputum 8-isoprostane, mean(SD) by treatment arm, difference in mean with 95% CI.

Comparisons will be made between the groups using ANCOVA (and post-hoc tests if significant differences are identified) will be used to detect difference in means adjusting for baseline values.

Will also be presented by comparison

Doc No: ST06-RD01 Page **16** of **29**

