3.3 Data completion schedule

Sputum (endotracheal secretions) samples will be collected at 3 time-points during the study; Day 0 (baseline - at randomisation), Day 3 and Day 7.

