5. SAMPLE SIZE CALCULATIONS

We plan to analyse sputum samples (at Day 0 and Day 3) collected from 340 patients enrolled in the MARCH trial from across participating ICUs. All consecutive patients recruited to MARCH will be approached to participate in the current study. The main MARCH clinical trial is recruiting a target of 1956 patients across the four arms of the study. Therefore, the proposed sample size for this study should be easily achieved given the anticipated recruitment for the MARCH study.

The sample size has been determined with statistical input from the Northern Ireland Clinical Trials Unit to generate significant differences in the primary outcome of percentage mucus solids in sputum samples of MARCH patients. A sample size of 85 in each of our treatment groups will have 90% power to detect a difference in means of 1.15% assuming that the common standard deviation is 2.3% using a two-group t-test with a 0.05 two-sided significance level. This is equivalent to an effect size of 0.5. Assuming approximately 5% dropout we will collect sputum samples from 360 patients recruited to MARCH trial (90 per arm). If the level of dropout is greater than anticipated, we will continue to collect sputum samples (matched Day 0 and Day 3) towards a target of 340 patients. Although there are no examples of mucus solids measurements in patients with ARF, the sample size generated above is based on mucus solid measurements evaluated in patients with cystic fibrosis and chronic obstructive pulmonary disease¹, the closest disease examples to ARF we could find in the literature.

Importantly, there are likely to be missing samples on day 7 due to extubation, discharge, or death. However, we intend analysing these samples as they will still provide important mechanistic information regarding the effect of both drugs on this day.

Doc No: ST06-RD01 Page **9** of **29**

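### The per-protocol ANCOVA adjusts only for Day 0 percent solids; chronic respiratory disease and humidification type are already collected and could be prespecified as covariates for a modest gain

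*SAP*

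**What the plan says.** Section 7 gives the method in general terms: ANCOVA "will be used to detect difference in means adjusting for baseline values". Section 8.5 makes the covariate explicit for the primary outcome: "will be used to detect difference in means adjusting for baseline values (Day O percentage mucus solid content (wt" (the parenthesis closes after the unit). Neither section names a further covariate, and no sensitivity or subgroup analysis brings one in.

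Section 8.3 lists two further baseline items for description only: "Does the patient have a pre-existing chronic respiratory condition?, n(%) by treatment" and "Type of humidification, n(%) by treatment arm". The shell table in Appendix 1 splits them into named chronic lung diseases (COPD, cystic fibrosis and bronchiectasis among them) and into none, heated, heat-moisture exchange and other.

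Four other statements bear on the point:

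- **Population (Section 7):** "The primary analysis will be conducted on outcome data from the per-protocol population". Section 4 defines that population by arm-specific rules: a UACM patient leaves it on starting a mucoactive from outside the trial, and the other arms require the complete dose.
- **Blinding (Section 6.2):** the trial is open label.
- **Disease and solids (Sections 7 and 5):** "Higher percentage weight indicates greater mucus solid content and is associated with disease", and the planning figures are "based on mucus solid measurements evaluated in patients with cystic fibrosis and chronic obstructive pulmonary disease".
- **Sampling (Section 3.3):** samples are taken at "Day 0 (baseline - at randomisation), Day 3 and Day 7".

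**The concern.** The aim in Section 1.3 is to learn whether the drugs hydrate airway mucus. Two recorded patient characteristics could also influence the Day 3 reading. For chronic respiratory disease, the SAP's own text supports the association. For humidification the argument is only one of plausibility: the circuit conditions gas going to the same airway, but the SAP does not say that its type affects solids.

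If either variable predicts Day 3 solids beyond the Day 0 value, leaving it out costs some precision. In a fully randomised comparison that would be the whole cost. Here the primary set is chosen after randomisation, by rules that differ between arms, in an unblinded trial, and it also needs a Day 3 sample. Patients with chronic lung disease could plausibly leave the arms at different rates, and the present model has nothing to offset that. If the baseline table then showed an imbalance, any adjustment would be post hoc and open to dispute.

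**Working it through.** **Step 1. Reproduce the plan's own figure.** Inputs from Section 5: difference 1.15 wt%, SD 2.3 wt%, two-group t-test, two-sided 0.05, power 90%.

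- n per group = 2 × (1.960 + 1.282)² × 2.3² / 1.15² = 84.1, rounded up to 85. The exact noncentral-t power at 85 is 0.8999, so the stated figure reproduces.
- With 5% dropout, 85 / 0.95 = 89.5, or 90 per arm and 360 in all, as stated.
- The calculation uses an unadjusted t-test, so omitting covariates takes nothing from the stated 90%.

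**Step 2. Gain from the two covariates.** The SAP gives no figure for the extra share of variance explained (R²) beyond the Day 0 value. I assume 2%, 5% and 10%, with a residual SD of 2.3 before they are added.

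- SE reduction = 1 − √(1 − R²)
- Equivalent extra patients = 340 / (1 − R²) − 340
- 95% CI half-width = 1.96 × 2.3 × √(1 − R²) × √(2/85)

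| Assumed extra R² | SE reduction | Equivalent patients | Power at 85 per group | CI half-width (wt%) |
|---|---|---|---|---|
| 0% | 0 | 0 | 90.0% | 0.691 |
| 2% | 1.0% | 7 | 90.6% | 0.685 |
| 5% | 2.5% | 18 | 91.4% | 0.674 |
| 10% | 5.1% | 38 | 92.7% | 0.656 |

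If Day 0 and Day 3 solids correlate at 0.5 (also assumed), the residual SD is 2.3 × √0.75 = 1.99. Power is then already 96.3%, and an extra R² of 5% or 10% raises it to 97.0% or 97.6%. The percentage fall in the SE is unchanged.

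**Step 3. Size of a chance imbalance.** For a yes/no factor with prevalence p and 85 per arm, the 95% limit of the between-arm difference is 1.96 × √(2p(1 − p)/85): 0.120 at p = 0.2 and 0.150 at p = 0.5. Multiply by an assumed effect on Day 3 solids that remains after Day 0 adjustment:

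- Effect 0.5 wt%: shift 0.06 (p = 0.2) to 0.08 (p = 0.5) wt%.
- Effect 1.0 wt%: shift 0.12 to 0.15 wt%.
- Effect 2.0 wt%: shift 0.24 to 0.30 wt%. At p = 0.5 this effect implies R² = 0.25 × 2.0² / 2.3² = 19%, beyond the range in Step 2.

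For comparison, the target difference is 1.15 wt% and the SE of a two-arm contrast is 2.3 × √(2/85) = 0.35 wt%. Chance shifts of this kind are already covered by the confidence interval.

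**Step 4. What cannot be computed.** The SAP gives no basis for estimating how far per-protocol exclusions would unbalance either factor. That part of the argument rests on Sections 4, 6.2 and 7, not on a number.

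**The case against.** The strongest reply is that nothing here is wrong. ANCOVA on the patient's own baseline is valid, the SAP promises no other covariate, and under randomisation omitting a prognostic variable does not bias a linear model. The Day 0 sample is taken at randomisation, so whatever lung disease and current humidification have already done to the mucus is in the Day 0 value; only an effect on the later course remains. No section says that humidification type affects solids, and Section 5 notes that no such measurements exist in acute respiratory failure. A yes/no chronic-disease item pools COPD and cystic fibrosis with lung cancer, interstitial disease and sarcoidosis. Randomisation is deferred to MARCH procedures, so any stratification on these factors cannot be seen. The gain is small and rests on assumed values.

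Nearly all of this stands. What does not fully carry over is the appeal to randomisation, because the primary set is selected afterwards by arm-specific rules without blinding.

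A reader might go further and infer that the planned analysis is biased or underpowered, or that humidification is an established source of variation left in the contrast. The documents support neither: the sample size reproduces, and the SAP gives no humidification effect. Nor would the adjustment capture a change of circuit after Day 0. Baseline type cannot show a later switch, and the post-entry items in Section 8.4 include no humidification variable.

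**Conclusion.** The point holds as a modest, cheap improvement in precision and robustness. The stated 85 per group and 90% power are unaffected. Over an assumed extra R² of 2% to 10% the SE falls by about 1% to 5%, and power at 85 per group rises from 90.0% to between 90.6% and 92.7%. If the two variables add nothing beyond the Day 0 value, the gain is nil and the loss trivial.

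The case is firmer for chronic respiratory condition, which the SAP's own text supports, than for humidification type, which is plausible only. Adjustment may partly reduce imbalance created by per-protocol selection. It would not correct that selection fully, and the choice of analysis population is a separate matter.

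**What to change.** In Sections 7 and 8.5, specify the Day 3 and Day 7 ANCOVAs for percent solids and for rheology (elasticity, viscosity, yield stress) with three baseline terms: the Day 0 value of the outcome, pre-existing chronic respiratory condition (yes/no), and baseline humidification type (heated; heat-moisture exchanger; none or other). Report the Day 0-only model alongside. State that the humidification term reflects baseline status only, and that the adjusted model is not offered as a full remedy for per-protocol selection.

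The cost is SAP wording and three model degrees of freedom (one for the yes/no item, two for the three-level item). No new data are needed. The SAP should also fix in advance how the few missing covariate values are handled, for example with a missing category, which would use a little more of the model.
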